## **Evaluation Design and Measurement.**

Assessments. Participants will complete assessments at baseline and one month. A blinded, trained research assistant will administer assessments at the bedside (baseline) and over the telephone (1-month). The assessments require under 30 minutes to complete. Subjects will receive an incentive of \$20 for completion of the 1-month assessments. The PI will also conduct an in-depth interview with the patient navigator to explore barriers to successful navigation.

Primary Outcome: whether a prescription for an FDA-approved smoking cessation medication was sent to the participants' pharmacy (Y/N, based on chart review)

Secondary outcomes: Self-reported smoking cessation at 3 months, utilization of smoking cessation medication, stage of change assessed at baseline and 3 months, according to the following categories: pre-contemplation, contemplation, preparation, or action. For each participant, we compare stage of change at baseline vs. 3 months. We will also measure level of nicotine dependence (baseline and 3 months), measured by the Fagerstrom Test for Nicotine Dependence, and use of other tobacco treatment support (3 months), defined as self-report of all tobacco treatment support received, including support from non-study sources, including the internet, during the 1-month study period.

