Retention: We expect to retain at least 60% of participants from baseline to 1-month follow-up, based on our prior experience conducting assessments at 3 (70% retention) and 6 months (76% retention) in similar populations. To maximize retention we will collect contact information including home address, phone, cell phone, beeper, e-mail, and phone numbers of three contacts. We will provide \$20 for completion of the 1-month assessment.

Patient Navigation Intervention: We base our intervention on the Social Contextual Model, a multi-level approach to health education which stresses the influence of life experiences (e.g. stress and financial problems) and social relationships (e.g. social networks and family roles) on the practice of health behaviors.

Participants will meet the navigator in person if she is available, or will be introduced by telephone. Participants will receive navigation from a trained navigator, based centrally in the Section of General Internal Medicine. The navigator has a BA degree, has extensive experience doing community health outreach, and has previously completed the University of Massachusetts "Basic Skills for Working with Smokers Online Course." Participants will receive up to ten hours of patient navigation, in person or over the phone, over a one-month period. We chose a two-hour intervention dose based on 1) a prior study of MI in low-income smokers and 2) our prior work studying navigation to promote smoking cessation. We have not designated a specific number of contacts, but allot a maximum of ten hours of patient navigation time per participant. The navigator will work flexible hours, contacting patients on evenings and weekends as necessary. Patient navigation contacts will involve individual counseling to help the patient achieve abstinence. We will adapt and incorporate into the PN script a modified version of the WE CARE Survey, which consists of 12 questions designed to: (1) identify six unmet material needs (inadequate education, employment, food security, housing, childcare, and household heat) by self-report (e.g., Are you employed?) and 2) determine whether participants would like assistance with each problem (e.g., If No, do you want help?). The survey takes less than five minutes to complete and has a test-retest reliability of 0.92.7 Thus, navigators will screen participants for social determinants of health which

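### Section 4 sets the single follow-up assessment at one month, but four secondary outcomes and the only named between-arm test are defined at 3 months

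*Combined protocol and SAP*

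**What the plan says.** Section 4 gives one month in six places.

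- Evaluation Design and Measurement, schedule: "Participants will complete assessments at baseline and one month".
- Same paragraph, mode of follow-up: "over the telephone (1-month", closing bracket omitted here.
- Same paragraph, $20 incentive: "for completion of the 1-month assessments".
- Secondary outcomes, recall window for other support: "including support from non-study sources, including the internet, during the 1-month study period".
- Retention: "We expect to retain at least 60% of participants from baseline to 1-month follow-up", and in the same paragraph a $20 payment tied to a 1-month assessment.

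Other text gives 3 months.

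- The secondary outcomes in Evaluation Design begin "Self-reported smoking cessation at 3 months, utilization of smoking cessation medication". Stage of change and the Fagerstrom score are set at baseline and 3 months. Other support is listed as "use of other tobacco treatment support (3 months", closing bracket again omitted.
- Section 3.1 repeats these definitions, with a 3-month recall window for other support.
- Section 4, Data Collection, places the telephone data collection 3 months after randomization.
- Section 8.4 schedules baseline and 3 months. Section 8.5 pays for a 3-month assessment.
- Section 11.3 compares the arms on cessation at 3 months.
- The Protocol Summary gives each subject 3 months of participation.

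**The concern.** Sections 4 and 8.4 each contain a near-identical schedule sentence, and the two sentences name different follow-up times. Section 4 also disagrees with itself, because its Data Collection paragraph and its own outcome definitions say 3 months. Within the definition of other support, the time point is 3 months and the recall window is one month.

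This goes beyond missing detail: following the Evaluation Design schedule would put the call at the wrong time. A 3-month call that was never made cannot be recovered later. Cessation, the only outcome with a named between-arm test, would be recorded at a time the analysis does not use. Retention bears on feasibility, the stated aim of the pilot, yet its expectation is given only for one month, with none for the 3-month assessment that the analysis needs.

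**Working it through.** There is no sample-size or power figure to reproduce. The check is a side-by-side reading with some simple arithmetic.

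**1. Count of references to the follow-up time**

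| Place | One month | 3 months |
|---|---|---|
| 3.1 outcome definitions | 0 | 6 |
| 4 Data Collection | 0 | 1 |
| 4 Retention | 2 | 0 |
| 4 Evaluation Design | 4 | 5 |
| 8.4 Assessments | 0 | 2 |
| 8.5 Cost/payment | 0 | 1 |
| 11.3 Statistical Methods | 0 | 1 |
| Total | 6 | 16 |

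The subject participation line in the Protocol Summary is not counted. Prior-study retention figures are not counted either.

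**2. Could both follow-ups be intended?** The Evaluation Design schedule and section 8.4 each list baseline plus one follow-up. The $20 is attached to a 1-month assessment in section 4 and to a 3-month assessment in 8.4 and 8.5. Section 8.4 gives $15 + $20 = $35, which equals the maximum in 8.5. There is no room for a second paid follow-up. An unpaid contact is not excluded by the cap, but none is described.

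**3. Outcomes affected.** Four secondary outcomes carry a 3-month time point: cessation, stage of change, Fagerstrom score and other support. The fifth, medication utilization, has no stated time point and is left out of the count. Assessments at 3 months under the Evaluation Design schedule: 0. Under Data Collection and 8.4: 1.

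**4. Size of the timing gap**

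- One month = 365.25 / 12 / 7 = 4.35 weeks.
- 3 months = 3 × 4.35 = 13.04 weeks.
- Difference = 13.04 − 4.35 = 8.7 weeks, for both the call and the recall window.

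**5. Retention.** The expectation is at least 0.60 × 50 = 30 participants. Its stated basis is "based on our prior experience conducting assessments at 3 (70% retention) and 6 months (76% retention) in similar populations". Applied to this trial, that is 0.70 × 50 = 35 and 0.76 × 50 = 38. Both exceed 30, so the experience already cited would support the same floor at 3 months.

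**6. Related items found on the way**

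- Section 8.5 prints $105 for the baseline assessment. Sections 4 and 8.4 say $15. As printed, $105 + $20 = $125, above the $35 maximum.
- The Protocol Summary gives a total study duration of 3 months. Recruitment of 12 weeks plus 13.0 weeks of follow-up is about 25 weeks. At the estimated 4 to 5 recruits per week, 50 participants take 50/5 = 10 to 50/4 = 12.5 weeks, giving a range of about 23 to 25.5 weeks.
- The navigation period is one month in section 4 and 3 months in the Protocol Summary and section 7.2.
- The navigation dose is two hours in section 4, ten hours in section 7.2, and both 3 and ten hours in the Protocol Summary. All three places also state a ten-hour maximum.

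**The case against.** The strongest reply is that the plan does contain a 3-month assessment. Sections 3.1, 8.4, 8.5 and 11.3 and the Data Collection paragraph all say so, and a careful reader would settle on 3 months. That is right. The loss of the four outcomes is conditional on staff following the Evaluation Design schedule, and the fault is a failure to reconcile section 4. It limits the severity but leaves the contradiction in place.

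The 16 to 6 tally overstates the evidence, since 11 of the 16 come from one outcome paragraph printed almost identically in 3.1 and 4. This stands. The better argument is that outcome definitions, procedures, payment and analysis agree with one another.

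One-month navigation, one-month follow-up and a one-month study period form a coherent set within section 4, so changing the follow-up alone could leave a new mismatch. This also stands: the navigation period has to be settled in the same amendment.

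Three smaller points are fair. The $105 may be a merged edit or an artefact of text extraction and should be checked against the source. The 25-week duration is approximate. The consent pages are not available, so whether participant-facing wording also needs changing cannot be seen. None of these touches the main point.

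**Conclusion.** The concern holds. Section 4 states a follow-up schedule that conflicts with its own outcome definitions and Data Collection paragraph, and with sections 3.1, 8.4, 8.5 and 11.3. Followed as written, the Evaluation Design schedule collects 0 of the 4 participant-reported outcomes at their defined time and places the call about 8.7 weeks early.

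This should be fixed, but it is not critical. The harm falls on secondary outcomes in a pilot whose aim is acceptability and feasibility. The primary outcome comes from chart review and does not depend on the call. No look-back window is stated for it, so whether a one-month or 3-month study period would alter it cannot be determined.

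The conclusion assumes a single paid follow-up, which is what both schedules and the $35 maximum indicate, and calendar months of average length.

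**What to change.** In section 4, change the six one-month references to 3 months, to match the outcome definitions and section 11.3: the retention follow-up, the payment in the Retention paragraph, the schedule sentence, the telephone assessment, the incentive, and the recall window for other support. The expectation of at least 60% can then be restated for 3 months on the experience already cited. If a one-month contact is also wanted, describe it as a separate contact and say whether it is paid.

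In the same amendment:

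- The investigators must reconcile the statements on navigation period and navigation hours in the Protocol Summary and sections 4 and 7.2. This review takes no view on which is right. The period should be settled together with the follow-up time.
- Check the $105 in section 8.5 against the source file and bring it into line with the $15 elsewhere and the $35 maximum.
- Define total study duration and state it as recruitment plus follow-up, about 25 weeks on the plan's own estimate.
- Give medication utilization a time point.

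The cost is a wording amendment with IRB review, and a check of whether the consent form needs the same changes. It adds no participants, staff, assessments or payment beyond the $35 already stated. The stated study duration lengthens from 3 months.

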## 5 Potential Risks and Benefits

#### 5.1 Risks

- (1) Loss of confidentiality: To minimize the risk of loss of confidentiality, the study coordinator will collect all data, and the study coordinator, data manager, and PI will be the only members of the team with access to the link between unique identifiers and patient data. The key will be stored on an encrypted server behind the university's firewall. Data will be stored on a secure server to which only designated individuals have access, thus providing a secure environment for all project data. The database will be backed up on a nightly basis. Any hard copy materials will be kept in a locked file in the PI's locked office. Any research staff who has access to patient health information will be trained in human subject's research that includes how to keep this kind of information private. Results will never be presented in any way where a patient could be identified.
- (2) Participant discomfort in answering sensitive questions: The surveys may ask some questions that are sensitive to the study participant. The participant will be told that he/she may refuse to answer any or all questions, and that refusal to

answer a question will not affect his/her medical care and will not keep him/her from participating in the rest of the study.

(3) Potential unknown risk: There may be unknown risks/discomforts involved. Study staff will update participant in a timely way on any new information that may affect their health, welfare, or decision to stay in this study.

#### 5.2 Potential Benefits

This research is being conducted with the primary goal of producing knowledge, and so the primary benefits to be gained are those related to the knowledge that the research may produce. An accurate understanding of the effects of this intervention on improving access to smoking cessation programs and leading to smoking cessation itself is crucial in reducing disparities.

## 5.3 Analysis of Risks in Relation to Benefits

In light of the tremendous benefits to public health and individual smokers of developing more effective smoking cessation programs, as well as our efforts, outlined above, to mitigate all risks associated with this study, we believe that this study presents a highly favorable risk-benefit ratio for participation.

## 6 Study Subject Selection

## 6.1 Subject Inclusion Criteria

In order to be eligible to participate in this study, an individual must meet all of the following criteria:

- 1) Hospitalized smokers at BMC
- 2) At least 18 years of age
- 3) Must smoke at least one cigarette per day in the past month
- 4) Able to speak, read, and understand English
- 5) Able and willing to comply with all study protocols and procedures
- 6) Having a PCP in Boston Medical Center
- 7) Possession of a telephone (home or cell)
- 8) Must have plans to quit smoking

#### 6.2 Subject Exclusion Criteria (See table 1)

An individual who meets any of the following criteria will be excluded from participation in this study:

- 1) Cannot give informed consent or participate in counseling due to psychiatric or cognitive impairment or communication barrier
- 2) Medical instability
- 3) Estimated life expectancy of <12 months

#### 7 Arms and Interventions

## 7.1 Comparator Arm (ENHANCED USUAL CARE):

Enhanced Traditional Care: Participants randomized to this group will receive a resource card that has information on quitlines, BMC's outpatient program number, and websites for smoking cessation.

#### 7.2 Intervention Arm:

Patient Navigation Intervention: We base our intervention on the Social Contextual Model, a multi-level approach to health education which stresses the influence of life experiences (e.g. stress and financial problems) and social relationships (e.g. social networks and family roles) on the practice of health behaviors.

Intervention Components and Content. Participants will meet the navigator in person if she is available, or will be introduced by telephone. Participants will receive navigation from a trained navigator, based centrally in the Section of General Internal Medicine. Our navigator has a BA degree, and has extensive experience doing community health outreach. Participants will receive up to ten hours of patient navigation, in person or over the phone, over a 3-month period. We chose a ten-hour intervention dose based on 1) a prior study of motivational interviewing in low-income smokers and 2) our prior work studying patient navigation to promote smoking cessation. We have not designated a specific number of contacts, but allot a maximum of ten hours of patient navigation time per participant. The navigator will work flexible hours, contacting patients on evenings and weekends as necessary. Patient navigation contacts will involve individual counseling to help the patient achieve abstinence from smoking. Navigators will also screen participants for social determinants of health which may be preventing them from quitting smoking, using an adapted version of a validated social determinants of health screening tool. Patient navigation intervention calls will use motivational interviewing (MI) strategies to do the following: (1) Assess stage of change for smoking cessation; (2) Assess and reinforce any prior abstinence from smoking and/or any efforts made to reduce or quit smoking; (3) Explore the patient's motivation to quit smoking, drawing on recent illness, financial situation, and family situation as appropriate; advise about the risks of smoking and benefits of quitting (4) Discuss past experience with utilizing cessation support; (5) Explore potential barriers to using smoking cessation medications (e.g. lack of trust, cost, misconceptions about treatment (e.g. that nicotine replacement therapy (NRT) is more harmful than cigarettes)); (6) Brainstorm strategies to address identified barriers; (7) Elicit commitment to accept another patient navigation counseling call, discuss timing.

## 8 Study Procedures

## 8.1 Screening and Recruitment

First, medical record (MR) will be accessed to determine (1) if patient is a current smoker (patients must be current smokers), (2) age of participant (must be age 18 or greater), (3) currently hospitalized on the general internal medicine or family medicine services or hospitalized within the past month, (4) have a primary care provider at BMC, (5) an estimated life expectancy of <12 months and (6) medical instability.

For patients that have not been excluded by MR review, the following questions will be asked to confirm eligibility:

How old are you? (must be  $\geq$  18)

Are you a current smoker? (smoked at least 1 cigarette per day in the past month)

Do you have a working telephone? (must have working telephone)

Do you read, understand or speak English? (must read, understand, and speak English)

Are you able and willing to provide informed consent? (must be willing and able to provide informed consent) When, if ever, do you plan to quit smoking cigarettes? (must have plans to quit smoking within 6 or more years)

The first contact could be made in-person prior to discharge, or over the phone, if patient has been discharged.

#### 8.2 Consent Procedures

In-person: The research assistant will approach potentially eligible participants and ask them if he /she can be asked a few screening questions. Subjects will be given at least several hours before they are discharged from the hospital to decide if they want to participate. After being found eligible, the research assistant will review the consent document with the potential participant. During the consenting process, she will describe the study and answer any questions the

participant may have. She will then ask all those who are willing to participate to sign the form. The consenting procedure will take place in a private exam room in the hospital.

Over the phone: If patients are discharged from the hospital, the Research Assistant will review the consent document with the potentially eligible participants over the phone. Following the consent document, she will describe the study and answer any questions the participant may have. If a person would like to think about it, they will be asked to contact us within 1 week if they are still interested in participating. If participant is interested in participating, the RA will mail participant two copies of the consent form with a prestamped envelope and have him or her mail back a signed version. No study procedures (except fo screening) will occur prior to receiving the signed consent.

#### 8.3 Randomization

Randomization will occur after RA obtains informed consent from the participant. Participants will be randomly allocated in a 1:1 ratio to the intervention or comparator arm.

## 8.4 Assessments

Participants will complete assessments at baseline and 3 months. A trained research assistant will administer these assessments either in-person or over the phone. The assessments require under 30 minutes to complete. Participants will receive an incentive of \$15 for completion of baseline assessment and \$20 for completion of the 3-month assessment.

## 8.5 Cost/payment

There is no cost associated with participation in the study beyond any costs normally associated with the care the patients are receiving at BMC.

Participants will receive up to \$35 to thank them for participating in the study. Participants will receive a \$105gift card for completing the baseline assessment and a \$20 gift card for completing the 3-month assessment.

## 9 Assessment of Safety and Data Safety Monitoring Plan (DSMP)

This study is not greater than minimal risk. Unanticipated Problems, Adverse Events, and protocol deviations will be reported to the IRB as required by IRB policies (http://www.bumc.bu.edu/ohra/hrpp-policies/hrpp-policies-procedures/#6.6.3).

The study monitor will be the Principal Investigator at Boston Medical Center/BU Medical Campus, and will report all adverse events and Unanticipated Problems to the IRB in compliance with IRB policy, Federal/State regulations, and sponsor requirements (as applicable).

## 10 Data Handling and Record Keeping

# 10.1 Confidentiality

All data files will be kept on a HIPAA-compliant secured shared drive with access restricted to project staff using password protected computers. Initially, research and medical records will be used to build the analytic databases. Each subject will be assigned a unique study identification number and all other identifiers will be removed as early as possible without compromising the conduct of the study. The linkage file between study identification number and medical record number will be stored separately on a password-protected server accessible only to the principal investigator, project manager and programmer/analyst. Confidentiality of patient information will be protected by using password-protected computers for all data analysis and management, as well as keeping confidential information printed on hard copies in locked file cabinets in the PI's locked office. Only project staff will have access to confidential

information and have been trained in compliance and working with protected health information. Study information will only be shared among project staff as needed to complete the study objectives using password-protected files on restricted-access secured shared drives.

## 10.2 Study Records Retention/Data and Safety Monitoring Plan

## **Study Records Retention.**

Study data will be kept for seven years after the study is completed. Paper materials will then be shredded and files will be deleted from study computers.

• PHI and the key to what unique identifier goes with what medical record number will be destroyed at the earliest opportunity, no later than five years after publication of the results (in aggregate anonymous format).

